## GLOSSARY

ACT	Artemisinin-combination therapy
AE	Adverse event
AL	Artemether-lumefantrine
ALT	Alanine transaminase (SGPT)
ART	Antiretroviral therapy
AS/AQ	Artesunate-amodiaquine
AST	Aspartate aminotransferase (SGOT)
AUC	Area under the curve
BID	Twice a day
CAB	Community Advisory Board
CBC	Complete blood count
CDC	Center for Disease Control
CI	Confidence Interval
C max	Maximum plasma concentration of a drug
C min	Trough serum concentration of a drug
Cr	Creatinine
CRF	Case report form
CYP3A4	Cytochrome p450 3A4
CYP2B6	Cytochrome p450 2B6
DAIDS	Division of AIDS
DHA	Dihydroartemisinin
DMC	Data Management Centre
DP	Dihydroartemisinin-piperaquine
DSMB	Data and Safety Monitoring Board
ECG	Electrocardiogram
EFV	Efavirenz
H	Hour
HFA	Height for age
Hg	Hemoglobin
HIV	Human Immunodeficiency Virus
HRPP & IRB	Human Research Protection Program and Institutional Review Board
HS-RDT	High sensitive rapid diagnostic test
IDRC	Infectious Disease Research Center
IPT	Intermittent preventive therapy (for malaria)
IRB	Institutional review board
ITN	Insecticide treated net
LAMP	Loop-mediated isothermal amplification
LBW	Low birth weight (<2500g)
LPV	Lopinavir
LPV/r	Lopinavir/ritonavir
LR	Lumefantrine
MGH	Masafu General Hospital
MOH	Ministry of Health
MU	Makerere University

NDA	Uganda National Drug Authority
NICHHD	National Institute of Child Health and Human Development
NIH	National Institutes of Health
NLME	Non-linear mixed effects
NNRTI	Nonnucleoside reverse transcriptase inhibitor
NRTI	Nucleoside reverse transcriptase inhibitor
NVP	Nevirapine
OR	Odds ratio
PCR	Polymerase chain reaction
PD	Pharmacodynamics
PI	Protease inhibitor
PK	Pharmacokinetics
PO	Oral
PQ	Piperaquine
PROMOTE	Prevention of Malaria and HIV Disease in Tororo
Q	Every
QTc	Corrected QT interval
QTcB	Corrected QT interval using Bazzett's correction
QTcF	Corrected QT interval using Fridericia's correction
QD	Once every day
RR	Relative Risk
SD	Single dose
SP	Sulfadoxine-pyrimethamine
TASO	The AIDS Support Organization
TDH	Tororo District Hospital
TS	Trimethoprim-sulfamethoxazole
UCSF	University of California, San Francisco
ULN	Upper limit of normal
UNAIDS	Joint United Nations Program of HIV AIDS
UNCST	Ugandan National Council for Science and Technology
WFA	Weight for age
WFH	Weight for height
WHO	World Health Organization

## EXALT TRIAL SCHEMA

### DESIGN:

Randomized open-label prospective pharmacokinetic and pharmacodynamic study of extended duration artemether-lumefantrine in HIV-infected children on EFV-based ART and HIV-uninfected children

### SAMPLE SIZE:

- 1) HIV-infected children with uncomplicated malaria on EFV-based ART
  - Up to 60 children enrolled into an intensive PK study of 3-day vs 5-day AL with 30 needed for each regimen\*.
  - Up to 100 children enrolled into a population PK study of 3-day AL and 5-day AL with 50 needed for each regimen\*.
- 2) HIV-uninfected children with uncomplicated malaria
  - Up to 100 children enrolled into an intensive PK study of 3-day vs 5-day AL with 50 needed for each regimen\*.
  - Up to 120 children enrolled into a population PK study of 3-day AL and 5-day AL with 60 needed for each regimen\*.

*\* participants will be enrolled from study sites in Uganda, including Tororo District Hospital (TDH) as the primary site, Masafu General Hospital (MGH) in Busia, and other centers.*

*\* individual participants can be enrolled into the intensive PK study for 2 episodes of malaria and can be enrolled into the population PK studies for 2 episodes to minimize the number of total participants needed.*

### POPULATION:

- 1) HIV-infected children on EFV-based ART aged 3 to 18 years.
- 2) HIV-uninfected children aged 6 months to 18 years.

### STUDY REGIMENS FOR PARTICIPANTS:

- 1) HIV-infected participants must be on efavirenz (EFV) + 2NRTI
- 2) All participants will be given either 6-dose or 10-dose AL over the course of the study for individual episodes of uncomplicated malaria. The order of administration will be via randomization.

### MALARIA CASE DEFINITION:

Uncomplicated malaria (all of the following)

- Fever (> 38.0°C tympanic) or history of fever in the previous 24 hours
  - Positive thick blood smear
  - Absence of complicated malaria
- Complicated malaria (any of the following)
- Evidence of severe malaria and parasitemia
  - Danger signs present and parasitemia
  - Parasite density > 500,000/μl

#### STUDY DURATION:

Up to 42 days for treatment of each malaria episode.

- Children will be eligible to participate in intensive PK sampling for up to two episodes of malaria. Children will be randomly assigned to either 3-day or 5-day regimens for each episode of malaria for the intensive PK sampling.
- Children will also be eligible to participate in the population PK sampling and again will be randomized to 3-day or 5-day regimens for each subsequent episode of malaria.
- Each child can participate in intensive and/or population PK evaluations for up to a total of 4 malaria episodes

#### HYPOTHESES:

- 1) 5-day AL will provide superior PK exposure and improved treatment outcomes compared to 3-day AL in HIV-infected EFV-treated children
- 2) 5-day AL in HIV-infected EFV-treated children will provide comparable PK exposure and outcomes to 3-day AL in HIV-uninfected children.
- 3) 5-day AL in HIV-uninfected children will provide superior PK exposure and improved treatment outcomes as compared to 3-day AL in HIV-uninfected children.

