#### PRIMARY OBJECTIVES:

- 1) To evaluate and compare the PK exposure between 5-day AL treatment and 3-day al treatment in HIV-infected children on EFV-based ART
- 2) To evaluate and compare the PK exposure of 3-day and 5-day AL treatment in HIV-infected children on EFV-based ART to 3-day AL treatment in HIV-uninfected children not on ART.
- 3) To evaluate and compare the PK exposure of 3-day and 5-day AL treatment in HIV-uninfected children not on ART.
- 4) To evaluate the pharmacodynamics of AL in the context of extended dose regimens and HIV infection.

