**1.1.3 Malaria and HIV in Uganda.** Uganda bears a heavy burden of both malaria and HIV. Although malaria prevention and control programs have reduced infections and mortality overall, Uganda still has one of the highest malaria transmission intensities in the world. In Tororo, the site of this proposal, children experience up to 2 to 6 malaria episodes per year, despite usage of bed nets and trimethoprim-sulfamethoxazole (TS) for those HIV-infected. For HIV, Uganda is lauded for prior success in stemming the HIV epidemic, but new infections are now on the rise. It is estimated that 2 million HIV-infected children will reside in sub-Saharan Africa in 2020. Thus, HIV-malaria co-infection remains common, with treatment complicated by multiple pharmacological factors that require field-based studies, such as those currently proposed in this renewal.

**1.1.4 Significant drug interactions occur between ART and ACT.** Both components of AL are extensively metabolized. Artemether undergoes rapid demethylation by cytochrome p450 3A4 (CYP3A4) and CYP2B6 to the active metabolite,

dihydroartemisinin (DHA), which undergoes further metabolism via UDP-glucuronosyltransferases (UGT). CYP3A4 is also responsible for metabolizing lumefantrine to desbutyl-lumefantrine (desbutyl-LR), and was shown by our group to be

Table 1	Comparison of AL PK exposure in HIV-infected children on ART compared to HIV-uninfected children (controls)		
	HIV-uninfected	HIV-infected	
	AL alone (control)	AL+EFV	
	GM; 95%CI (n=52)	GM; 95%CI (n=31)	GMR, EFV/Control
AR_AUC 0-8	120 (97.6-147) a	48.5 (37.2, 63.1)	0.40***
DHA_AUC 0-8	212 (176, 256) a	62.9 (49.2, 80.3)	0.30***
LR_AUC 0-∞	270 (232, 313)	130 (107, 157)	0.48***
LR Half-life b	64.3 (52.0, 121)	23.7 (21.8, 46.0)	0.37***
Intensive and sparse PK (n=363 episodes)			
	Median (IQR), n=186	Median (IQR), n=48	MR, EFV/Control
LR C 7d	340 (257, 531)	111 (63, 192)	0.30***
LR C 14d	86 (59, 137)	BLQ (BLQ,BLQ)	<1***
LR C 21d	BLQ (BLQ, 63)	BLQ (BLQ,BLQ)	<1**

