The ACTs are the most important drugs for the treatment of uncomplicated malaria. Despite their widespread use globally, fundamental questions remain for assuring their optimal use in our most vulnerable populations, especially for children in the context of interacting medications or malnutrition. Our results to on ACT drug interactions are striking and reveal that HIV-infected children treated with AL have a wide range of antimalarial exposure depending on their ART. Compared to no ART, lopinavir/ritonavir (LPV/r)-based ART increased lumefantrine PK exposure >2-fold, while efavirenz (EFV)-based ART, first-line for children >3 years of age, dramatically reduced exposure to artemether, the active dihydroartemisinin metabolite, and lumefantrine. Importantly, these PK changes were associated with a 4-fold higher risk of recurrent malaria after treatment with AL in children receiving EFV compared to those receiving LPV/r. These findings suggest that AL dosing should be modified for children receiving EFV. We propose that extending AL dosing from 3 to 5 days will offset these changes. We will study an extended AL regimen, rather than a higher dose, as we know lumefantrine absorption is dose-limited (Section 1.1.8). This strategy should be useful for other conditions causing low exposure, such as pregnancy, and in the setting of emerging resistance.

We will conduct our study in the malaria-endemic region of Eastern Uganda in both Tororo and Busia where our team has long standing experience directing field-based PK/PD studies in the most relevant populations. We will utilize a combination of state-of-the-art intensive and population PK designs and drug assay methods to determine drug exposure and study associations between exposure and specific malaria outcomes including recurrent malaria.

Rationale for this study is summarized below:

- Dosing guidelines for children have historically relied on studies carried out in adults despite knowledge that children exhibit distinct physiological characteristics that impact how drugs are handled by their body
- Improper dosing may compromise care of acute infection but more importantly contribute to develop of resistance
- We have shown that interactions between AL and EFV greatly altered levels to BOTH artemether and lumefantrine, and put patients at risk for treatment failure.
- Extended dosing intervals of AL may overcome lower exposure that is found in patients concomitantly taking EFV.

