### 9.4 Intensive PK study

#### 9.4.1 Sample Size

Using measures of mean AUC and its coefficients of variation (CV) from our studies and the literature, the intensive arms of the study are powered to detect differences in ACT AUC between all study groups (3-day AL vs 5-day AL) with  $n=30$  for each group of HIV infected children. To assure adequate age-matched HIV uninfected children,  $n=50$  is used for the group of HIV uninfected children. Figure 1 and Table 8. 50 HIV-uninfected children provides for adequate subjects  $< 3$  years and  $\geq 3$  years of age as HIV-infected children receiving EFV-based ART is restricted to  $\geq 3$  years of age. In addition, the same size of 50 will permit PK/PD of the extended regimen in younger children  $< 3$  years of age. At least 30 HIV uninfected children must be between 3-10 years of age.

For comparisons where  $n=30$  in both groups, there will be 80% power to detect a difference in AUC of 35% or more, given an overall Type I error of 0.05, a Bonferroni correction for multiple comparisons, and with assumption that the coefficient of variation (CV) for all AUC's is 35-38%. For the HIV-uninfected children with  $n=50$ , further distinctions based on age can be determined as well as further enhancement of exposure-response analysis.

Although many children are likely to be studied for both the 3-day and 5-day regimens, it is not likely that *all* children will provide results for both. However, all analyses will account for repeated measures/correlated data that occur from participants enrolled into multiple arms.

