#### 9.4.2 Intensive PK Analysis

PK parameters for each subject will be estimated using non-compartmental analysis (NONCMP) and follow a linear up-log down trapezoidal rule in conjunction with first-order input (WinNonlin). PK parameters, including the elimination rate constant  $\lambda_z$  and  $t_{1/2}$  will be estimated, with  $t_{1/2}$  calculated as  $\ln_2/\lambda_z$ . AUC will be estimated as the  $AUC_{0-8h}$  or  $AUC_{0-24h}$  (as results permit) for artemether/DHA and the sum of  $AUC_{last}$  (AUC to the

end of the sampling period) and  $AUC_{last-\infty}$  (from the end of sampling to infinity) for lumefantrine/ desbutyl-lumefantrine. PK parameters will be compared between groups of interest (Figure 1 and Table 8) using a two-sided unpaired t-test for two-group comparisons, and ANOVA for multi-group comparisons. If PK parameters are found to have skewed distributions and data transformations do not induce symmetry, rank-based tests will be used. To enhance comparison between 3-day and 5-day AL, peak concentrations collected on Days 0-4 will be integrated using population methods. The following groups will be compared:

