## 9.5 Population PK study

### 9.5.1 Sample Size

160 episodes of malaria in HIV-infected children and 220 episodes of malaria in HIV-uninfected children (up to 4 episodes per child including up to 2 involving intensive sampling) are more than sufficient to obtain population PK parameter estimates for both groups of children with good precision. Outcomes will be assessed in children in both the intensive and population PK studies, as such, sample sizes reflect the sum of children enrolled in each arm for each type of PK sampling. Thus, total sample sizes will be 80 to 110 children per arm. Using WinPOPT®, the standard errors (SE) of all population PK parameters, including variability parameters, will be <20% of their means, except for the interindividual variability of  $k_a$ , for which the SE is estimated to be 32% of its mean. Based on our recent study from Tororo, where a 42-day recurrence rate of 47% was observed in those on EFV-based ART, we will have 80% power to detect a 20% difference in recurrence rates between 3-day and 5-day arms. Notably, in our previous exposure-outcomes, with 50 to 70 children in each ART arm and 184 children not on ART, a 2.1-fold change in AUC between those on EFV and lopinavir/ritonavir translated to a 2.7-fold increase in risk for reinfection. In other words, the anticipated increase in AUC between 5-day and 3-day AL of 1.7-fold increase in exposure is expected to translate to a clinically relevant change in risk in a similar number of subjects.

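### Hypothesis 2 claims comparable exposure, but Section 9.4.2 plans only difference tests and gives no rule for comparability, and for lumefantrine the protocol's own figures imply a ratio near 0.8 that those tests often miss

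*Combined protocol and SAP*

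**What the plan says.** The trial schema lists three hypotheses. The first and third are superiority claims. The second is a similarity claim: "5-day AL in HIV-infected EFV-treated children will provide comparable PK exposure and outcomes to 3-day AL in HIV-uninfected children". The matching primary objective is neutral: "To evaluate and compare the PK exposure of 3-day and 5-day AL treatment in HIV-infected children on EFV-based ART", set against 3-day AL in HIV-uninfected children. Section 1.2 is firmer: "We propose that extending AL dosing from 3 to 5 days will offset these changes".

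For the analysis, Section 9.4.2 compares PK parameters "using a two-sided unpaired t-test for two-group comparisons, and ANOVA for multi-group comparisons", with rank-based tests if the data stay skewed. On size, Section 9.4.1 says that with n=30 in both groups "there will be 80% power to detect a difference in AUC of 35% or more", at an overall Type I error of 0.05 with a Bonferroni correction (divisor not stated) and a CV of 35-38%. Neither section gives an equivalence or non-inferiority margin, or a confidence-interval rule, for AUC or for recurrence.

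The figures that bear on the claim are Table 1 (Section 1.1.4), with EFV/control ratios under 3-day AL of 0.48 for lumefantrine, 0.40 for artemether and 0.30 for DHA, and Section 9.5.1, which refers to "the anticipated increase in AUC between 5-day and 3-day AL of 1.7-fold increase in exposure".

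Section 9.1 plans the 5-day EFV v 3-day control contrast. Table 8 row 2 carries that title but names the 3-day EFV arm as the comparison group.

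**The concern.** A difference test can show that two groups differ. Failing to show it is not evidence that they are alike, and it becomes more likely as the data become noisier. Hypotheses 1 and 3 fit the planned test; Hypothesis 2 does not.

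The gap matters because the protocol's own inputs do not point to parity for lumefantrine. They point to a shortfall of about a fifth, smaller than the 35% difference for which the study is sized. The results are meant to inform treatment guidelines (Section 3.1.1), and this contrast tells readers whether two more days of AL restore exposure in children on EFV. Without a rule set in advance, a real deficit and true similarity could produce the same report: no significant difference.

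**Working it through.** **Inputs.** n=30 per group (Table 8); CV 35-38% and overall alpha 0.05 with Bonferroni (Section 9.4.1); ratio 0.48 and confidence intervals (Table 1); 1.7-fold gain (Section 9.5.1). Assumed: a divisor of three, because Table 8 has three rows, and analysis on the log scale.

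**1. The plan's own power.** Log SD = √ln(1+CV²) = 0.340 at CV 35% and 0.367 at CV 38%. SE of the log ratio = SD × √(2/30) = 0.0878 and 0.0948. For a ratio of 1.35, ln 1.35 = 0.300, so the noncentrality is 3.42 and 3.16. With 58 df and two-sided alpha 0.05/3, power is 83% and 76%, which brackets the stated 80%. The plan's figure is reproduced, so the same set-up is used below.

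**2. Predicted lumefantrine ratio, 5-day EFV / 3-day control.** 0.48 × 1.7 = 0.82. By dose count, 0.48 × 10/6 = 0.80. Parity would need a gain of 1/0.48 = 2.08-fold.

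**3. Chance that the planned test is non-significant at a true ratio of 0.80.** |ln 0.80| = 0.223.

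| Spread | SE | Noncentrality | Non-significant at 0.05 | At 0.05/3 |
|---|---|---|---|---|
| CV 35% | 0.0878 | 2.54 | 29% | 47% |
| CV 38% | 0.0948 | 2.35 | 36% | 54% |
| Table 1 (log SD 0.53) | 0.137 | 1.63 | 64% | 79% |

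The last row takes log SD = ln(upper/lower) × √n / (2t). Controls: ln(313/232) = 0.2995, n=52, giving 0.538. EFV: ln(157/107) = 0.3834, n=31, giving 0.523. These equal a CV of about 56-58%, well above the planned 35-38%.

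**4. Sensitivity to the AUC definition.** Section 9.4.2 sums AUC to the last sample and its extrapolation to infinity, and Appendix A times the samples from the last dose. If the AUC starts there, the gain is not 1.7. With one compartment, 12-hourly doses and Table 1's EFV half-life of 23.7 (read as hours), each interval leaves a fraction 0.5^(12/23.7) = 0.704. The gain is (1 − 0.704^10)/(1 − 0.704^6) = 0.970/0.878 = 1.10, and the ratio is 0.48 × 1.10 = 0.53. The deficit is then larger and easily detected.

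**5. Artemether and DHA.** Their AUC is over 0-8 h or 0-24 h (Section 9.4.2), sampled around the last dose (Sections 5.1.1 and 6.7.1). More doses need not raise it. If Table 1's ratio of 0.40 persists for artemether, then even with the log SD of about 0.73 implied by its intervals (assuming the headed n's), non-significance occurs in under 1% of trials at 0.05 or 0.05/3. For DHA at 0.30 it is lower still.

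**6. What a margin would demand.** The documents give none. With an illustrative 0.80-1.25 and a 90% CI, n=30 per arm gives 62% power at CV 35% and 51% at CV 38% if the true ratio is 1.00; 80% power needs about 41 to 47 per arm. With an illustrative 0.70-1.43, power at parity is 98% to 96%, but 53% to 48% at a true ratio of 0.82.

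**The case against.** Four objections deserve an answer.

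- *The plan never says that non-significance means comparable.* True. The primary objective speaks only of evaluating and comparing. A reader might infer that a non-significant p-value is the sole evidence planned for Hypothesis 2, but Section 9.5.2 also quantifies the EFV effect on clearance and bioavailability, relates exposure to outcome and simulates regimens. What stands is narrower: none of these analyses says what result would count as comparable.
- *The shortfall may be hidden for all three analytes.* A reader might multiply 0.40 and 0.30 by 10/6, predict 0.67 and 0.50, and conclude that artemether and DHA deficits could also be masked. The documents do not support this. The planned AUC for these analytes describes the last dose, not the course, so dose count does not scale it. Only the supplementary population step for Days 0-4 peaks looks across the course.
- *The 1.7-fold gain is not tied to the planned AUC or to children on EFV.* This also stands. It is the sponsor's own figure, but if it does not apply, the lumefantrine ratio is further from parity and more easily detected. The hypothesis is then less plausible, and the test is less likely to miss the deficit.
- *A margin may be unreachable at n=30.* Also fair. That argues for choosing between a margin and estimation now; it does not make a difference test adequate.

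**Conclusion.** The point holds as a missing decision rule, and its numerical force lies with lumefantrine. Hypothesis 2 is a similarity claim with no test of similarity. If the anticipated 1.7-fold gain applies to the planned AUC, the protocol's figures imply a shortfall of 18-20%. At a true ratio of 0.80 the planned test would miss it 29% to 36% of the time unadjusted and 47% to 54% with Bonferroni over three. Those figures rest on the plan's CV; with the spread in the sponsor's earlier data they become 64% and 79%. A non-significant result is therefore weak evidence of comparability.

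For artemether and DHA the issue is different. Table 1's ratios, if they persist, conflict openly with Hypothesis 2 and with the proposal in Section 1.2 that the extension will offset the interaction.

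The outcomes half of Hypothesis 2 also has no margin. It is not quantified here because the documents give no recurrence rate for controls.

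**What to change.** - **Section 9.4.2.** For 5-day EFV v 3-day control, make the geometric mean ratio with its 90% CI the primary summary for each analyte. State that non-significance will not be read as comparability.
- **Decision rule.** Conclude comparable only if the CI lies inside a margin that the sponsor justifies and fixes before PK assay results are analysed. Otherwise report the ratio as the residual deficit. Alternatively, reword Hypothesis 2 as estimation of that deficit. Treat the recurrence half of the hypothesis the same way.
- **Clarifications.** Say whether the lumefantrine AUC runs from the first or the last dose, and state the Bonferroni divisor.
- **Table 8 row 2.** Reconcile the listed 3-day EFV arm with the row's title and Section 9.1.

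The reporting change and the rewording need no added children or samples. The cost is that the comparability claim becomes harder to make. At the illustrative 0.80-1.25 margin, 30 per arm gives only 51% to 62% power at true parity, so keeping a claim at a margin that tight would call for more children. Estimation wording may be the realistic choice.

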#### PRIMARY OBJECTIVES:

- 1) To evaluate and compare the PK exposure between 5-day AL treatment and 3-day al treatment in HIV-infected children on EFV-based ART
- 2) To evaluate and compare the PK exposure of 3-day and 5-day AL treatment in HIV-infected children on EFV-based ART to 3-day AL treatment in HIV-uninfected children not on ART.
- 3) To evaluate and compare the PK exposure of 3-day and 5-day AL treatment in HIV-uninfected children not on ART.
- 4) To evaluate the pharmacodynamics of AL in the context of extended dose regimens and HIV infection.

